Title: Brain and Gut Plasticity in mild TBI or post-acute COVID Syndrome Following Growth Hormone Therapy

Principal Investigator: [name]., Internal Medicine, UTMB

Co-I: [name]., Internal Medicine, UTMB

Co-I: [name]., Pediatrics, UTMB

Co-I: E. [name]., Internal Medicine, UTMB

Institution: The University of Texas Medical Branch at Galveston

Sponsors: The Moody Endowment

Sealy & Smith Foundation

Specific Aims

Increasing evidence suggests the gastrointestinal (GI) microbiome is altered in patients with history of mild traumatic brain injury (mTBI). In this project, we propose to characterize the GI microbiome in patients with a history of mTBI or post-acute COVID syndrome complex (PASC) in comparison to healthy controls. Furthermore, we propose to investigate the potential effects of recombinant Human Growth Hormone (rhGH, given as somatropin, a polypeptide hormone (GENOTROPIN)) on the GI microbiome, fatigue, cognition, brain activation, and brain morphology in individuals with a history of mTBI or PASC.

Specific Aim 1a. To characterize the GI microbiome in patients with a history of mTBI compared to controls. - mTBI Baseline vs. Control Baseline - Fecal samples for determination of the GI microbiome will be collected monthly from mTBI subjects and healthy controls over 6 months to examine the diversity of the microbiome within and between groups. **Outcomes:** Genus, species, q-PCR for selected marker organisms.

Specific Aim 1b. To characterize the GI microbiome in patients with a history of mTBI based on presence of *Prevotella spp.* - mTBI *Prevotella spp.* positive Baseline vs. mTBI *Prevotella spp.* negative Baseline - Fecal samples for determination of the GI microbiome will be collected monthly from mTBI subjects over 6 months to examine the diversity of the microbiome within and between groups. **Outcomes:** Genus, species, q-PCR for selected marker organisms

Specific Aim 2. To characterize the GI microbiome in patients with a history of post- COVID-19 syndrome (PASC) compared to arm 2 controls. - PASC Baseline vs. Control Baseline - Fecal samples for determination of the GI microbiome will be collected monthly from PASC subjects over 6 months to examine the diversity of the microbiome within and between groups. **Outcomes:** Genus, species, q-PCR for selected marker organisms.

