Specific Aim 3. To determine whether growth hormone therapy-induced changes in fatigue and cognition correlate to changes in the GI microbiome. - mTBI/PASC Baseline (month 0) vs. mTBI/PASC Month 6 – Changes in GI microbiome of mTBI or PASC patients will be correlated to fatigue/cognition symptom resolution in response to growth hormone treatment. Healthy

controls will provide control data. Controls will not receive rhGH treatment. **Outcomes:** Changes in genus, species, Questionnaires (GSRS (GI), MoCA (cognition), BFI and MFSI (fatigue)).

Secondary Aims and Symptom-Related Outcomes and Assessment of Body Composition and Metabolism:

Specific Aim 4a. To determine whether growth hormone therapy alters mood, sleep quality, and quality of life. Mood, sleep, and quality of life will be measured at baseline (month 0) and month 6. (POMS (mood/QOL), QOL-AGHDA (QOL of growth hormone (GH) deficiency), PSQI (sleep), FPQ (food preferences)).

4b. To determine whether growth hormone therapy alters body composition and muscle function. Skeletal muscle mass, as derived from lean body mass determinations, and fat mass will be measured using dual energy x-ray absorptiometry (DEXA) at baseline (month 0) and month 6. (DEXA, Biodex, 6 min walk).

4c. To determine whether growth hormone therapy alters resting energy expenditure. Resting energy expenditure (REE) will be measured using indirect calorimetry at baseline (month 0) and month 6.

Background and Significance

Annually 1.5 million children and adults experience trauma to the head and brain that results in a traumatic brain injury (TBI). While TBI are classified as severe, moderate, or mild based upon the Glasgow Coma Scale (GCS), of the more than 1.5 million people who experience a TBI each year, as many as 90% sustain a mild TBI (mTBI) (1). mTBI can occur during organized sport (football, soccer), home recreation (bike riding, skateboarding), and as a result of a motor vehicle accident or other physical traumatic event. The term 'mild TBI' is misleading as we now know that a significant proportion of mTBI patients suffer from significant impairments or disabilities for many years following the initial brain injury. These include, "foggy brain," short-term memory loss, (1) impaired conversational abilities, and inability to organize daily activities. Together, this symptom complex renders many individuals unable to function in school or maintain a job.

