Notably, the cluster of symptoms associated with post-COVID syndrome include profound fatigue and cognitive dysfunction, which are strikingly consistent with BIAFAC. While studies are underway to understand the details of the mechanism causing BIAFAC and why GH treatment alleviates symptoms in these patients, we are intrigued that the symptom phenotype with post-COVID patients overlaps with many BIAFAC symptoms. It is possible that post-COVID syndrome may be addressed through similar treatment strategies including the potential for prebiotic/probiotic enhancement of microbiome health.

Therefore, in the current study we will assess the GI microbiota in individuals with a history of mTBI or PASC and fatigue. Each participant's baseline will serve as an individual control. An additional and critical control dataset that will be used for comparisons will be provided by analysis of the GI microbiome from healthy controls. Furthermore, we will investigate whether treatment with recombinant Human Growth Hormone (rhGH) will create changes in the gut flora producing microbiomes more similar to those expected in healthy controls and whether these changes correlate with the expected improvements in fatigue, cognition, brain activation, and brain morphology in the mTBI or PASC patients.

Experimental Design and Methods

Enrollment

TBI subjects: To address **AIM 1a** and **AIM 1b** we will study subjects with a history of mild TBI enrolled into either **arm 1** (n=25) or **arm 2** (n=25) for a total of (**n=50**).

Healthy Controls: To address **AIM 1** and **AIM 3** we will study healthy control subjects enrolled into either **arm 1** (n=25) or **arm 2** (n=25) for a total of (**n=50**).

[figure not shown]
PASC subjects: To address **AIM 3** we will study subjects with a history of COVID-19 and PASC symptoms enrolled into **arm 3** (**n=25**).

ARM 1: mTBI and Household Controls

Subjects. We will study subjects (aged 18-70 years) with a history of mild TBI (n=25) and their household controls (aged 18 years and up) (n=25). mTBI subjects will undergo a 6-month intervention of rhGH therapy (See Figure 1). Household controls will be asked to participate in questionnaires, blood draws (amino acid analysis), and fecal sampling (GI microbiome analysis). Household controls will not receive any growth hormone treatment.

mTBI group

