Before and at completion (month 6) of the rhGH intervention of their mTBI subject partners, household controls will report to the UTMB Institute for Translational Sciences (ITS) Clinical Research Center (CRC) for testing, which will consist of questionnaires of food preferences and gastrointestinal health and blood sampling for measurement of amino acid levels, hormones, and metabolites which will be drawn before and 90 minutes (+/- 10 minutes) after a standardized meal. In addition, fecal samples for the analysis of the GI microbiome will be collected monthly for the duration of the study, as well as questionnaire assessing gastrointestinal health. The monthly fecal sampling

History of PASC
Brief Fatigue Inventory (BFI) BFI ≥ 3 (Symptomatic)
Glucagon Stimulation Test Peak GH < 10 ng/mL
rhGH 0.4 mg/ day
Baseline Test (t = month 0) • DEXA • REE • Cognitive Function • Functional and Perceptual Fatigue • 6 min walk • Questionnaires • Fecal Sampling / GIQ • Nasal Sampling • Amino Acid Determination
Monitor Visit (t = month 1) • IGF-1 • Fecal Sampling / GIQ
(t = month 2) • Fecal Sampling / GIQ
(t = month 3) • Fecal Sampling / GIQ
(t = month 4) • Fecal Sampling / GIQ
(t = month 5) • Fecal Sampling / GIQ
Post Test (t= month 6) • DEXA • REE • Cognitive Function • Functional and Perceptual Fatigue • 6 min walk • Questionnaires • Fecal Sampling / GIQ • Nasal Sampling • Amino Acid Determination
(t = month 9) • Fecal Sampling / GIQ • Questionnaires
(t = month 12) • Fecal Sampling / GIQ • Questionnaires • Glucagon Stimulation Test

Figure 3. ARM 3: Study Design. Patients with a history of PASC, fatigue of ≥ 3 on the BFI and GH < 10 ng/mL will undergo 9 months of GH replacement therapy. Post study measures will take place at month 6. Subjects will collect fecal samples and fill out a GI questionnaire (GIQ) at months 0, 1, 2, 3, 4, 5, 6, 9 and 12. Subjects will repeat the glucagon stimulation test at month 12..

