Healthy control subjects will report to the UTMB Institute for Translational Sciences (ITS) Clinical Research Center (CRC) for testing at baseline and month 6. Testing will consist of questionnaires of food preferences and gastrointestinal health and blood sampling for measurement of amino acid levels, hormones, and metabolites which will be drawn before and 90 minutes (+/ 10 minutes) after a standardized meal. In addition, fecal samples for the analysis of the GI microbiome will be collected monthly for the duration of the study, as well as questionnaire assessing gastrointestinal health. The monthly fecal sampling will occur +/- 7 days from the expected date based on the baseline study visit. The post study (month 6) will occur +/- 7 days from the expected date based on the baseline study visit. A member of the study team will contact the subject each month to coordinate fecal sample transport to UTMB, check for adverse events and overall well-being, and ensure compliance and ongoing consent.

PASC Group (Arm 3)

PASC subjects will undergo 9 months of rhGH treatment. Before and at (month 6) of the rhGH intervention, PASC subjects will report to the UTMB Institute for Translational Sciences (ITS) Clinical Research Center (CRC) for testing, which will consist of cognitive function assessment (MoCA), determination of lean mass and fat mass using DEXA, resting energy expenditure, functional testing including leg strength and 6 minute walk test, fatigue measurements, and questionnaires of mood and quality of life, gastrointestinal health, sleep, and food preferences. Blood sampling for measurement of amino acid levels, hormones, and metabolites will be drawn before and 90 minutes (+/- 10 minutes) after a standardized meal. In addition, fecal samples for

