- Montreal Cognitive Assessment (MoCA). The Montreal Cognitive Assessment (MoCA) (20) is a rapid assessment of cognition. The MoCA consists of 9 questions with the following subcategories: visuospatial/executive, naming, memory, language, abstraction, delayed recall and orientation. The MoCA has been used extensively to detect cognitive impairment in many conditions, including head trauma. Version 7.1 will be used at the Month 0 testing and Version 7.2 will be used at the Month 6 testing.

GI microbiome. The GI microbiome will be assessed using fecal samples collected at monthly time points (baseline (month 0), month 1, month 2, month 3, month 4, month 5, and month 6). Additional fecal samples will be collected for Arm 3 PASC subjects at month 9 and month 12. If a mTBI subject sustains an additional TBI during the study period, the study will be extended to collect fecal samples for an additional 6 months. If a PASC subject is infected with COVID again during the study months 9 - 12, the study will be extended to collect an additional sample at month 13 and month 15. Subjects will provide fecal samples as described below. Fecal samples will be collected +/- 7 days from specified time point based on baseline (month 0) study. Subjects will be allowed to collect monthly fecal samples at home. Samples will be stored at 4°C until transferred to UTMB (on/+ 3 days after collection). Subjects will be given a tutorial on how to properly collect the fecal sample. They will be given a handout from the manufacturer of the collection kit with step by step instructions. They will also be shown a video of the collection process supplied by the kit manufacturer. https://www.youtube.com/watch?v=ytr_hmJdHqM&feature=youtu.be&rel=0

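### Every patient takes MoCA form 7.1 first and 7.2 second, so any difference in form difficulty cannot be separated from the mean pre/post MoCA change

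*Combined protocol and SAP*

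**What the plan says.** The Cognitive Assessment part of the study procedures schedules cognitive testing at month 0 and month 6 only. Under Montreal Cognitive Assessment it fixes the form by visit: "Version 7.1 will be used at the Month 0 testing and Version 7.2 will be used at the Month 6 testing". No alternation, random order, equating step or equivalence data is given.

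The MoCA is listed for the mTBI patients in Arms 1 and 2 and the PASC patients in Arm 3, all of whom inject rhGH. It is not listed for controls. The household controls report for testing "which will consist of questionnaires of food preferences and gastrointestinal health and blood sampling for measurement of amino acid levels, hormones, and metabolites". For the Arm 2 healthy controls, "Testing will consist of questionnaires of food preferences and gastrointestinal health and blood sampling for measurement of amino acid levels". The detailed control procedures add fecal samples but no cognitive test.

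On the use of the MoCA:
- The Specific Aims introduction proposes to study the effects of rhGH "on the GI microbiome, fatigue, cognition, brain activation, and brain morphology in individuals with a history of mTBI or PASC".
- Specific Aim 3 sets out the contrast "mTBI/PASC Baseline (month 0) vs. mTBI/PASC Month 6" and lists among its outcomes "Questionnaires (GSRS (GI), MoCA (cognition), BFI and MFSI (fatigue". The analysis it describes is a correlation of microbiome change with fatigue and cognition change.
- The Therapeutic Rationale says that each participant's "baseline will serve as an individual control", and asks "whether these changes correlate with the expected improvements in fatigue, cognition, brain activation, and brain morphology".
- Statistical Considerations plans repeated-measures ANOVA for species abundances and for secondary symptom-related outcomes, at a 0.05 level with multiple-testing correction. It does not mention the MoCA, and it names no method of correction.

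**The concern.** An alternate form at the second visit is a reasonable guard against item recall. The difficulty is only that the order is the same for everyone. If form 7.2 is a little easier or harder than 7.1, the average MoCA change moves by that amount. Nobody takes the forms in the other order, and no untreated person takes them at all, so nothing in the data would show it. Age or other covariates cannot help, because form and visit are the same variable.

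At stake is the reading of mean MoCA change, on the only cognitive test listed, in a plan that expects cognition to improve.

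**Working it through.** **Figures in the plan.** The documents give no effect size, SD, power or sample size for the MoCA, so there is no stated figure to reproduce. Inputs taken from the documents are the fixed form order, two visits, 25 treated patients per arm (50 mTBI, 75 with PASC) and α = 0.05. Form differences and SDs of change below are assumptions.

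**1. Fixed order.** Let μ be the mean change from everything except form (rhGH, practice, time, regression to the mean), and δ the expected score on 7.2 minus that on 7.1, taken as the same at both visits. Every patient's expected change is μ + δ. With patient effects, visit and form in the model, the design matrix has rank 26 of 27 columns at n=25, 51 of 52 at n=50 and 76 of 77 at n=75. Visit and form correlate 1.0, and μ and δ cannot be separated.

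**2. Balanced order.** The 7.1-then-7.2 group estimates μ + δ and the reverse group μ − δ.
- Half the sum of the two group means is μ; half the difference is δ. The matrix is full rank (27, 52 and 77).
- In 20,000 simulated trials per setting (δ = 0.5 or 1.0, μ = 0, SD 2.5), bias in this average was about 0.005 point or less, and the rejection rate was 4.9% to 5.3%.
- Coding matters. With order coded 0/1, the intercept is the mean change in the reference order, μ + δ or μ − δ, and keeps the whole form bias: 0.50 point in simulation with δ = 0.5 and μ = 0. Coding −1/2, +1/2 makes the intercept the equally weighted average.

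**3. Aim 3 correlation.** Adding a constant to every MoCA change leaves a Pearson correlation unchanged (0.356 before and after in a simulated check). Balancing the order without adjusting for it would add ±δ to individual changes and shrink the correlation by SD/√(SD² + δ²). At SD 2.5 this is 2.5/√(6.25 + 0.25) = 0.98 for δ = 0.5, and 2.5/√(6.25 + 1) = 0.93 for δ = 1. Adjusting for order removes this.

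**4. Illustrative size.** Two-sided paired t-test, uncorrected α = 0.05, no drug effect, noncentrality = shift × √n / SD. Ranges run from SD 3 to SD 2.

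| Total non-drug shift | n=25 | n=50 | n=75 |
|---|---|---|---|
| 0 | 5% | 5% | 5% |
| 0.5 point | 13–22% | 21–41% | 30–57% |
| 1 point | 36–67% | 64–93% | 81–99% |

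The plan intends a multiplicity correction. If, as an assumption, this were Bonferroni over the four Aim 3 instruments (0.05/4 = 0.0125), a 0.5-point shift would give about 4–9% at n=25 and 9–22% at n=50.

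Balancing the order removes only the form share of a 0.5-point shift. At uncorrected 5%:
- all form: back to 5%;
- half form, half practice: 7–9% at n=25, 9–14% at n=50;
- all practice: unchanged;
- form −0.5 and practice +0.5: the two cancel under the fixed order (5%), and balancing exposes the practice shift (13–22% at n=25).

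**5. Precision at n=25, SD 2.5.**
- Fixed order: 95% half-width 2.064 × 2.5/√25 = 1.032 points.
- Order groups of 13 and 12: SE = 2.5 × √(1/13 + 1/12)/2 = 0.5004, and 2.069 × 0.5004 = 1.035 points.

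**The case against.** The strongest reply is that the one analysis in which the plan clearly places the MoCA, the Aim 3 correlation, is untouched by a constant form shift. A test of mean MoCA change is inferred: the repeated-measures ANOVA is for symptom-related outcomes, and the heading that uses those words stands over Aim 4, whose instruments do not include the MoCA. This stands. What remains is that Aim 3 is headed as a month 0 versus month 6 contrast and that cognition is expected to improve, so a mean-change summary is a natural output.

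It is also fair that the percentages rest on assumptions, and that they describe a total non-drug shift rather than a form difference. They illustrate the uncontrolled before/after design as much as the form order. A fixed order does give every patient the same baseline form. Cautious reporting would cover form, practice, time and regression to the mean together; it would still leave in place a bias that can be removed at almost no cost.

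Three stronger readings are tempting and are not supported:
- *The forms differ, so an observed improvement would be an artefact.* Nothing in the documents shows a difference, or equivalence.
- *Balancing the order would let mean change be read as an rhGH effect.* It would not: the comparison is still each patient with their own baseline.
- *Giving controls the MoCA would make the rhGH effect estimable.* That would need form effects, practice effects, time trends and regression to the mean all to be equal in patients and controls. Patients are selected on a BFI score of at least 3 and a stimulated GH peak below 10 ng/mL, and controls are not, so equality cannot be assumed.

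**Conclusion.** The concern holds in a limited form and is minor. As written, mean MoCA change equals the change from all other causes plus any form difference, and no analysis of the planned data can split the two. That is a property of the design and needs no assumption about size. How much it matters is unknown, because the documents give no form difference, direction or SD of change; the percentages above are illustrations under assumed shifts and SDs, before multiplicity correction. The Aim 3 correlation is not biased if the form difference is constant across patients; it could be affected only if that difference varied with ability or between pooled groups. Form order is a small and avoidable part of the larger limit of an uncontrolled before/after comparison.

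**What to change.** 1. For patients not yet tested, randomise MoCA form order in balanced blocks within each arm: half 7.1 then 7.2, half 7.2 then 7.1.
2. Estimate mean MoCA change as the equally weighted average of the two order groups, with order coded −1/2, +1/2 rather than read from a 0/1 intercept. Adjust for order in the correlation with microbiome change.
3. Report mean MoCA change as an uncontrolled pre/post change, not as an rhGH effect. This applies whether or not the order is changed, and is the only step left if testing is complete.

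The cost is an allocation list, one model term and a negligible loss of precision (half-width 1.032 to 1.035 points in the example). The documents do not say whether patients have already been tested. If some have, order will be partly confounded with enrolment period or arm. For example, with all 25 Arm 1 patients in the fixed order and Arm 2 split 13/12, order and arm correlate 0.56 in absolute value, the variance inflation is 1/(1 − 0.562²) = 1.46, and the form difference is estimated from Arm 2 alone.

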- Food Preference Questionnaire (FPQ). General food preferences will be assessed using a modified questionnaire. The food preference questionnaire requires participants to rate their liking of 62 individual foods on a 5-point Likert scale, ranging from “not at all” to “a lot”. Participants are instructed to select ‘N/A’ if they are not familiar with - or have no memory of - having tried a food item. Food preference scale scores for six food categories (Vegetables, Fruit, Meat/Fish, Dairy, Snacks, and Starches) are obtained by summing the single food preference item scores within each food category and dividing this sum by the number of items on the list. FPQ will be measured at month 0 and month 6 by TBI subjects. PASC subjects complete the FPQ at months 0, 6, 9 and 12. If a mTBI subject sustains an additional TBI during the study period, the study will be extended for an additional 6 months. An additional questionnaire will be collected at the end of the 6 month period. . If a PASC subject is infected with COVID again during the study months 9 - 12, the study will be extended to collect an additional questionnaires at month 13 and month 15.
- Gastrointestinal Symptom questionnaire. Gastrointestinal symptoms will be monitored monthly using the Gastrointestinal Symptom Rating Scale (GSRS). The GSRS is a 15-item questionnaire. Each question has a seven-point Likert-type scale where 1 represents absence of symptoms and 7 represents very troublesome symptoms. The GSRS will be measured each time a fecal collection is completed. If a mTBI subject sustains an additional TBI during the study period, the study will be extended for an additional 6 months. The GSRS will be collected monthly during the 6 month extension. . If a PASC subject is infected with COVID again during the study months 9 - 12, the study will be extended to collect an additional questionnaires at month 13 and month 15.

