tube for the first collection, they will scoop another small amount of fecal material with the same spatula and transfer it to a prepared cryogenic freezer tube containing sterile PBS (without Ca/Mg) and sterile glycerol. The tube will be closed and shaken for a minimum of 30 seconds to mix with the stabilization liquid. Samples will be labeled with the subject's unique code and stored at 4°C until transported to University of Texas Medical Branch. Samples will then be frozen at -80°C and stored until the molecular analysis is completed. After initial analysis, if the sample is considered useful (representative of the average control subject), it may be thawed, diluted in saline and used either to mix in a mathematical ratio to create a synthetic community or to be directly transplanted into germ free mice. If the sample is considered not useful (not representative of the average control subject) for fecal microbiome transplant into germ free mice, the sample will be destroyed.

- Questionnaires. Questionnaires will be completed to assess general food preferences and gastrointestinal symptoms. Time points for the collection of the questionnaires is included in each description.

- Food Preference Questionnaire (FPQ). General food preferences will be assessed using a modified questionnaire. The food preference questionnaire requires participants to rate their liking of 62 individual foods on a 5-point Likert scale, ranging from "not at all" to "a lot". Participants are instructed to select "N/A" if they are not familiar with - or have no memory of - having tried a food item. Food preference scale scores for six food categories (Vegetables, Fruit, Meat/Fish, Dairy, Snacks, and Starches) are obtained by summing the single food preference item scores within each food category and dividing this sum by the number of items on the list. FPQ will be measured at month 0 and month 6.
For Arm 1 only: If the mTBI subject sustains an additional TBI during the study period, the study will be extended for both the mTBI and household control for an additional 6 months. An additional questionnaire will be collected at the end of the 6 month period.

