Given the data acquired from two PASC subjects under IRB 20-0361 that have shown indistinguishable profiles to those of BIAFAC communities as well as remarkably reduced GH responses to GST, we expect that the Power calculations explained in this section (above) will also apply to PASC. Because PASC is a recent consequence to the pandemic no data exist to complete Power calculations beyond those of syndromes like BIAFAC that present with similar symptoms. We therefore have proposed enrollment of at least 25 PASC subjects to compare to 25 normal controls already included in this protocol.

For quantifiable (primary) outcomes such as abundances of individual species in the GI microbiome and (secondary) symptom related outcomes, a standard repeated measure ANOVA model will be used. When possible, age and other covariates will be brought into the model to reduce variability and account for random differences between the two groups. Significance tests will be performed at the $\alpha=0.05$ level, and multiple testing corrections will be used to account for potential Type I error rate inflation. Nonparametric, generalized linear, and transformed response models will be considered as necessary to alter the model to account for deviations from standard assumptions (normality, linearity, etc.). Current data support statistical outcomes being established with group sizes similar or slightly larger size than our previous study.

The graph below is based on group difference in *Alistipes onderdonkii*. Power calculations were performed using t-tests with G*Power (two-groups, two-sided, $\alpha=0.05$, Version 3.1.9.2, Germany). Effect size in this case was 1.184.

Below is a list of organisms we identified previously and which were used to conduct the power analyses for the present study. Please note that the intestinal flora includes an incredibly diverse system of organisms and at this time it is difficult to accurately predict which organisms will be included in the biome shifts we expect to see. Therefore, additional organisms may be included in the final microbiome comparisons between mTBI patients and household control subjects. Further power analyses will be conducted using the data collected during this investigation.

Target	n = 20 (10/group)	n=30	n=40	n= 50 (25/group)
Alistipes onderdonkii	70.7%	87.9%	95.4%	98.4%
Desulfovibrio	60.4%	79.3%	89.9%	95.4%
Prevotella spp	97.5%	99.8%	100.0%	100.0%
Akkermansia	64.8%	83.2%	92.6%	96.9%

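### The food preference score allows N/A answers but keeps them in the denominator, so each N/A lowers the category score, by the fraction m/k when m of k listed foods are N/A

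*Combined protocol and SAP*

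**What the plan says.** The FPQ is described twice in the combined protocol and SAP: under the study procedures for mTBI and PASC subjects, and under those for household and healthy controls. Both descriptions give the same scoring rule.

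- Participants "rate their liking of 62 individual foods on a 5-point Likert scale".
- They choose N/A "if they are not familiar with - or have no memory of - having tried a food item".
- Scores for six food categories come from "summing the single food preference item scores within each food category" and "dividing this sum by the number of items on the list".

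The instrument is called a modified questionnaire and no reference is given, so these sentences are the only scoring rule available. Neither description states the numeric coding of the five answers, gives N/A a value, takes N/A items out of the divisor, or sets a minimum number of rated items. By contrast, the BDI-II description does settle a scoring edge case, namely what to do when a respondent marks more than one statement for an item.

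Specific Aim 4a names the FPQ among its instruments: "PSQI (sleep), FPQ (food preferences". The Statistical Considerations deal with outcomes of this kind in one clause, "secondary) symptom related outcomes, a standard repeated measure ANOVA model will be used", and contain no rule for N/A or missing items.

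**The concern.** The numerator and the divisor count different things. The numerator can include only foods that received a rating. The divisor counts every listed food. A category score meant to express liking therefore also depends on how many foods the person does not know or cannot recall. Two people who like the foods they know equally well get different scores if one of them uses N/A more often.

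What is at stake is the interpretation of a named secondary outcome. The Aim 4a question for the FPQ is whether scores change between month 0 and month 6 under growth hormone. The FPQ is also completed by controls at the same two visits and is the only food-preference measure taken in both patients and controls, so a group comparison is possible. Either comparison can be distorted by the pattern of N/A answers.

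**Working it through.** The plan states no FPQ score, variance or power, so there is no figure of its own to reproduce. The check is of the scoring formula.

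**Inputs**

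- From the FPQ descriptions: 62 foods, six categories, a five-point scale, N/A allowed, and a divisor equal to the number of listed items.
- Assumed: k = 10 items per category. An equal split gives 62/6 = 10.3, but the actual split is not stated. One N/A costs 1/k of the score, so a smaller category loses more per N/A and a larger one less.
- Assumed: item coding of 1–5 or 0–4, since none is given.
- Assumed for illustration: the numbers of N/A answers (m). The documents give none.

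**Formula**

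Let L be the mean rating over the k − m rated items.

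- Sum of item scores = (k − m)L
- Score as written = (k − m)L/k
- Score over rated items = (k − m)L/(k − m) = L
- Difference = −(m/k)L

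**One visit, k = 10, L = 4**

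| N/A answers (m) | Score as written | Score over rated items | Shortfall |
|---|---|---|---|
| 0 | 40/10 = 4.0 | 4.0 | 0% |
| 1 | 36/10 = 3.6 | 4.0 | 10% |
| 2 | 32/10 = 3.2 | 4.0 | 20% |
| 3 | 28/10 = 2.8 | 4.0 | 30% |
| 5 | 20/10 = 2.0 | 4.0 | 50% |

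**Dependence on the coding**

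- Under 1–5, a person who gives the lowest rating to every food they know (L = 1) and has m = 2 scores 8 × 1/10 = 0.8, which is below the scale minimum of 1.
- Under 0–4, an N/A counts exactly like the lowest liking answer. With L = 3 and m = 2 the score is 8 × 3/10 = 2.4. There is no shortfall only if L = 0.
- Only a coding centred on zero would alter the direction, and nothing in the text suggests one.

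**Dependence on what the list means**

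If the divisor were all 62 foods, the category sums for m = 0 and m = 3 would give 40/62 = 0.645 and 28/62 = 0.452. The ratio is 28/40 = 0.70, the same 30% shortfall.

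**Effect on comparisons, k = 10**

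- Stable N/A use: with m = 2 at both visits and L rising from 4.0 to 4.5, the true change is 0.5. The score changes by (8 × 4.5 − 8 × 4)/10 = 0.4. The change shrinks by m/k = 20%.
- Changing N/A use: with L = 4 at both visits and m falling from 3 to 1, the true change is 0. The score changes by 9 × 4/10 − 7 × 4/10 = 3.6 − 2.8 = 0.8.
- Two groups with equal liking of 4, one with m = 3 and the other with m = 1, would differ by the same 0.8.

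**The case against.** The strongest reply is that the FPQ text is a short summary, that a scoring sheet may exist, and that the team may already intend to divide by the items rated. Nothing in the documents says so. The divisor is stated, the same sentence appears in both places, and an analyst who follows it obtains the lower score. It is fair, however, that the documents do not assign N/A a value. A reader might infer that an unfamiliar food is deliberately scored below the lowest liking answer. That does not follow: the effect arises from the fixed divisor, and N/A falls below the lowest answer only under 1–5 coding.

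A second reply is that Aim 4a compares each subject with their own baseline, and the set of foods a person does not know may be much the same six months later. This stands in part. Stable N/A use mainly shrinks change and does not create it.

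A reader might also infer that patients will use N/A more than controls because memory impairment belongs to the syndrome, or that N/A use will fall under treatment and mimic a benefit. The documents do not support either as a finding. They describe short-term memory loss, whereas the N/A option concerns foods the person does not know or does not remember ever trying, and nothing links the two. No N/A rate is given for any group or visit. Arm 1 controls share the patient's household and Arm 2 controls are matched on age and sex, which should reduce, though not remove, differences in familiarity. No aim states a patient-versus-control hypothesis for the FPQ.

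Finally, dividing by rated items is not perfectly neutral. It measures liking among tried foods and may overstate liking of a category if the untried foods are ones the person avoids. That is a real but small cost, and the resulting score has a clear meaning.

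**Conclusion.** The scoring rule is wrong as written in both FPQ descriptions. Each category score falls short of the mean liking of rated foods by the fraction m/k under 1–5 or 0–4 coding. With an assumed 10 items per category, that is 10% for one N/A and 50% for five. The direction rests only on a non-negative item coding. The percentages also rest on the assumed category size and N/A counts.

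The size in this trial is unknown, and so is whether the error differs between patients and controls or between visits. Differential bias is a possibility to guard against, not something the documents show. The consequence is confined to a secondary outcome: the FPQ plays no part in the sample size or the primary microbiome outcomes. The correction is still worth making because it is specific and nearly free.

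**What to change.** In both FPQ descriptions, define each category score as the sum of the item scores divided by the number of items actually rated in that category, excluding N/A. Prespecify a minimum number of rated items below which the category score is missing. Half the items is a common convention; the sponsor may choose another, provided it is fixed before analysis. State the numeric coding of the five answers in the same place.

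The cost is a sentence or two in two places. No new data are needed, and questionnaires already completed can be rescored provided the item-level answers were kept. The small downside, that the score then describes liking among tried foods only, should be stated where the score is defined.
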